3.0 PROTOCOL SUMMARY

Title	Combining Pregabalin (LYRICA®) with Lofexidine (LUCEMYRA™): Can it Increase the Success of Transition to Naltrexone?						
Short Title	Pregabalin and Lofexidine for opioid withdrawal						
Protocol Version	7.0						
Phase	Phase 2						
Methodology	Double-blind placebo-controlled parallel group clinical trial						
Study Duration	24 months						
Study Centers (3)	 University of Pennsylvania Center for Studies of Addiction in Philadelphia Pennsylvania Columbia University in New York City, New York Mountain Manor in Baltimore, Maryland 						
Objective (Primary)	To investigate whether pregabalin-Lyrica® (PGB) combined with Lofexidine-Lucemyra® (LFX) can reduce opioid withdrawal-related subjective effects						
Objective (Secondary)	To investigate, if the PGB/LFX combination can increase the proportion of patients with an opioid use disorder (OUD) who complete detoxification and transition to antagonist treatment with extended- release injectable naltrexone VIVITROL® (XR-NTX)						
Number of Subjects	90 subjects. 60 randomized to PGB/LFX; 30 to PGB-PLA/LFX						
Inclusion Criteria	 Male and/or female subjects ≥ 18 years of age Meet DSM-5 criteria for an Opioid Use Disorder with physiologic features. Have 2 or more of the 11 DSM 5 criteria for opioid disorder including tolerance and withdrawal features in the last 12 months Interested in opioid antagonist treatment Have used opioids in 20 of the past 30 days Have a stable address in the local area; not planning to move; have documents for ID check Absence of medical or psychiatric conditions that are likely to interfere with study participation Have a 12 lead ECG demonstrating a QTc ≤450 msec and a QRS interval ≤120 msec. The site PI has the final determination for inclusion into the study for ECGs unless there is a question of QT prolongation or other factors (QTc/Fri uses the Fridericia formula (QTc = QT/RR(1/3)). If consultation is needed, the PENN cardiologists and the medical monitor should be contacted. If female, have a negative pregnancy test, and uses adequate contraception if of childbearing potential 						
Exclusion Criteria	 Current psychotic disorder (bipolar I, schizophrenia, major depression with psychotic features,) as defined by the MINI An alcohol, benzodiazepine, or other sedative disorder with physiological features that require medication for detoxification History of allergy or other serious adverse event due to treatment with pregabalin, XR-NTX, or lofexidine 						

Pending incarceration in the next 30 days Homicidal or otherwise behaviorally disturbed requiring immediate attention. High Risk for suicide as determined by answering 'yes' to questions 4 and/or 5 on C-SSRS at screening Blood pressure <90 mm Hg (systolic) or <60 mm Hg (diastolic). If this value is out of normal range, the investigator and a study clinician will decide subject inclusion or exclusion on a case-by- case basis Heart rate and/or pulse<50 bpm at screening-sitting An Estimated Glomerular Filtration Rate eGFR<90 mL/min/1.73m² A history of, or current seizure disorder (excluding childhood febrile seizures) Inability to read and/or understand English. For example, does not understand the informed consent as demonstrated by failing to answer 9/10 questions correctly on the guiz Pregnant or breastfeeding Currently taking sympathomimetic drugs, or a thiazolidinedione antidiabetic An ALT and/or AST that is at > 4X the top limit of normal A Child-Pugh score >7 Currently receiving opioids for pain management In a treatment study where medication was administered in the last 30 days. Currently using medications that are known to be strong or moderate inhibitors of CYP2D6 such as fluoxetine, paroxetine, mirabegron, bupropion, quinidine, terbinafine, cimetidine, cinacalcet, duloxetine, or fluvoxamine In a methadone maintenance or buprenorphine treatment program within the last 30 days Pregabalin (PGB) or PGB-PLA given orally at a *starting* dose of up to 400 mg on day 1, up to 600 mg daily on Day 2 through Day 4, tapered to 100 mg daily Study Product, Dose, by Day 7; Lofexidine (LFX) starts at 1.62 mg on day 1, 2.16 Day 2 through Day Route, Regimen 4, tapering to 0.72 mg by Day 7. After starting dose on Day 1, both study drug doses can be reduced or withheld depending upon patient's clinical observations for Days 1-7. On day 8, subjects are offered an injection of XR-NTX if they provide a urine sample that is negative for opioids, buprenorphine, and fentanyl, and pass a naloxone challenge. All subjects, regardless of whether or not they receive XR-NTX, will be given a list of referrals and help with making an appointment for follow-up treatment when they leave the inpatient detoxification program. The following "comfort" medications are suggested for treatment of withdrawal symptoms that are not suppressed by study medications: ondansetron 4 mg or 8 mg tid PO PRN for nausea and vomiting, trazodone 100 mg HS PRN insomnia, loperamide 2 mg qid PO PRN diarrhea, and a non-steroidal such as **Comfort Medications** Ibuprofen 600 mg qid PO PRN for aches and pains or acetaminophen 650 mg (2 tablets 325 mg) PO gid PO PRN, cyclobenzaprine 5 mg tid PO PRN for muscle aches and pains, and hydroxyzine 25 mg qid PO PRN anxiety. In cases of QTc prolongation that are not >550ms or judged to require stopping study medications, diphenhydramine 50 mg hs PO PRN may be used for insomnia, and trimethobenzamide 300 mg gid PO PRN for nausea.

Outpatient screening is used to determine eligibility for the study. It will consist of the 30 days prior to inpatient admission for study detoxification and treatment. On day 1 of inpatient treatment subjects will be randomized to PGB/LFX or PGB-PLA/LFX for a 7-day detoxification. On day 8, if the patient completes **Duration of subject** detoxification, continues to be interested in XR-NTX treatment, provides a urine, participation and and passes a naloxone challenge, he/she will be offered one injection of XR-NTX before hospital discharge. This injection of XR-NTX is optional. If retests must be medication administration done, such as a repeat of the naloxone challenge, all subjects are eligible to remain inpatient until Day 9. All subjects, whether they receive XR-NTX or not. will be referred to continuing care and asked to return to the research outpatient clinic on days 10 and 15 for follow-up visits. Subjects who cannot find a provider may be offered an additional XR-NTX injection up to 5 weeks after the Day 8 injection. Reference therapy PGB-Placebo plus lofexidine The primary outcome is reduction in subjective withdrawal as measured twice/day using the Short Opiate Withdrawal Scale (SOWS- Gossop). SOWS scores range from zero to 30. Groups will be compared on 10 or more repeated SOWS responses during inpatient treatment using linear mixed-effects regression models. The SOWS total will be regressed on a three-level factor for site, and a two-level factor for pregabalin dose, with random intercept and correlated residuals and a random slope included if necessary for fit. Contrasts Statistical between the combined groups will be estimated from this model. Methodology The secondary outcome is an ordinal response indicating completion of detox and receipt of antagonist treatment, with levels (1) failure to complete detox, (2) completion of detox with failure to receive antagonist treatment, and (3) completion of detox and receipt of antagonist treatment.

Note: Study medication will be provided in blister packs that are prepared by the PENN Investigational Drug Service and shipped to all three study sites. For the University of Pennsylvania, each blister pack will have a patient randomization number and the dosing schedule for each time on each inpatient study day, as summarized in the Study Schematics 4.0 below. For the two external sites, patient randomization will be generated by the site pharmacy or designated unblinded person, who receives the blister packs from the PENN Investigational Drug Service with the dosing schedule for each day.

The doses for each time of each day will be in separate compartments. Lofexidine will be 0.18 mg pink tables; pregabalin or pregabalin placebo will be in capsules. Blue capsules will contain 100 mg pregabalin or placebo; green capsules will contain 25 mg pregabalin or pregabalin placebo. These medications have not been used together and it is likely that doses will need to be held or reduced due to side effects. The most likely side effect from lofexidine is hypotension and/or bradycardia. The most likely side effect from pregabalin is sedation. Thus, in the event of hypotension, the next scheduled dose of lofexidine can be reduced or withheld. A similar adjustment can be made for excessive sedation (POSS score of 3 or 4; difficult to arouse, slurred speech, etc.) For the PENN site, medication counts will be done by the Investigational Drug Service (IDS) pharmacy for each subject. For sites outside PENN, medication counts will be done by the site or site pharmacy.

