- **7.5.6** XR-NTX and Renal Impairment. A pharmacokinetic analysis indicated that mild renal insufficiency (creatinine clearance of 50-80 mL/min) had little or no influence on XR-NTX pharmacokinetics and that no dosage adjustment is necessary. Pharmacokinetics of XR-NTX have not been evaluated in subjects with severe renal insufficiency, thus individuals with severe renal abnormalities will not be included in this study.
- **7.5.7 XR-NTX and Gender.** In a study of healthy subjects (n=18 females; 18 males), gender did not influence the pharmacokinetics of XR-NTX.
- **7.5.8 XR-NTX and Drug-Drug Interactions.** Studies evaluating drug-drug interactions have not been performed.
- **7.5.9** XR-NTX and Reversal of Blockade for Pain Management. In an emergency situation, suggestions for pain management are regional anesthesia or non-opioid analgesics. If opioids are required, they must be provided in a setting where establishment and maintenance of a patent airway and assisted ventilation are readily available from persons trained in the use of anesthetic drugs and management of respiratory depression.

- **7.5.10** Depression and Suicidality. In controlled trials among patients with alcohol dependence, AEs of a suicidal nature (ideation, attempts and completed suicides) were infrequent, but more common in patients treated with XR-NTX than placebo (1%). In some cases, suicidal thoughts or behaviors occurred after study discontinuation but in the context of an episode of depression that began while the patient was on the medication. Two completed suicides occurred in alcohol treatment studies, both in patients treated with XR-NTX, and depression-related events were more common in patients treated with XR-NTX than in those on placebo (1%). However, two studies that have specifically examined the relationship between depression and XR-NTX treatment found that depression and anxiety decrease in association with detoxification and naltrexone treatment (Mysels et al, 2011; Krupitsky et al, 2016)
- **7.5.11** Naltrexone Contraindications. Patients should not receive XR-NTX if they are taking opioid analgesics; have current opioid dependence; are in opioid withdrawal; failed a naloxone challenge or have a positive urine screen for opioids; exhibited hypersensitivity to naltrexone, PLG, carboxymethylcellulose, or any other components of the diluent; or have acute hepatitis or liver failure.

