10.2 EXCLUSION CRITERIA

- 1. Current psychotic disorder (bipolar I, schizophrenia, major depression with psychotic features,) as defined by the MINI
- 2. An alcohol, benzodiazepine, or other sedative use disorder with physiological features that require medication for detoxification
- 3. History of allergy or other serious adverse event due to treatment with pregabalin, XR-NTX, or lofexidine
- 4. Pending incarceration in the next 30 days
- 5. Homicidal or otherwise behaviorally disturbed requiring immediate attention
- 6. High risk for suicide as determined by answering 'yes' to questions 4 and/or 5 on C-SSRS at screening
- 7. Blood pressure <90 mm Hg (systolic) or <60 mm Hg (diastolic). If this value is out of

33

- normal range, the investigator and study Clinician will decide subject inclusion or exclusion on a case-by-case basis, (can use manual blood pressure check if considered necessary)
- 8. Heart rate and/or pulse<50 bpm at screening-sitting
- 9. An Estimated Glomerular Filtration Rate eGFR<90 mL/min/1.73m²
- 10. A History of, or current Seizure disorder (excluding childhood febrile seizures)
- 11. Inability to read and/or understand English. For example, unable to understand the informed consent as demonstrated by failing to answer 9/10 questions correctly on the guiz
- 12. Pregnant or breastfeeding
- 13. Currently taking sympathomimetic drugs, or a thiazolidinedione antidiabetic
- 14. An ALT and/or AST test that is ≥4X the upper limit of normal
- 15. A Child-Pugh score >7
- 16. Currently receiving opioids for pain management
- 17. In a treatment study where medication was administered in the last 30 days
- 18. Currently using medications that are known to be strong or moderate inhibitors of CYP2D6 such as fluoxetine, paroxetine, mirabegron, bupropion, quinidine, terbinafine, cimetidine, cinacalcet, duloxetine, or fluvoxamine
- 19. In a methadone maintenance or buprenorphine treatment program within the last 30 days

Note: Subjects who fail screening for other than medical or severe psychiatric reasons can be reevaluated by staff at a later date.

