13.4 SAFETY OUTCOMES

- 13.4.1 Suicidality. We will compare the groups on presence of active suicidal ideation on the basis of the C-SSRS, which will be administered daily. We define Active Suicidal Ideation to be an endorsement of either Question 4 (active ideation without plan) or 5 (active ideation with plan). If there is sufficient variability in these repeated binary outcomes, we will compare the groups using a mixed effects logistic regression model, similar to the linear mixed effects models described above for the primary outcome; if variability is too low, we will use a (non-mixed-effects) logistic regression model to compare the groups on proportion of participants reporting active ideation at any time in the period
- **13.4.2 Sedation.** The POSS will be administered four times a day on dose days, yielding a set of repeated measures on the POSS score for each participant. We will compare the groups on this score, using linear mixed effects models similar to those described above for the primary outcome.
- **13.4.3** Elevated Creatine Kinase. On day 8 of detoxification, participants will be classified as having elevated creatine kinase if their level is more than three times their screening level. We will compare groups on this response using a logistic regression model with site and group as explanatory variables.
- **13.4.4_Edema**. We will compare groups on the proportion of participants whose study medications were discontinued due to peripheral edema, using a logistic regression model with site and group as the explanatory variables.

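### With no events in an arm, the low-event fallback for suicidality in Section 13.4.1 gives no finite odds ratio or usable Wald interval, and the section names no test

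*Combined protocol and SAP*

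**What the plan says.** Section 3.0 lists this exclusion, and Section 10.2, item 6 repeats it: "High Risk for suicide as determined by answering 'yes' to questions 4 and/or 5 on C-SSRS at screening".

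Section 13.4.1 defines the outcome on the same items: "We define Active Suicidal Ideation to be an endorsement of either Question 4 (active ideation without plan) or 5 (active ideation with plan"). The main analysis is conditional: "If there is sufficient variability in these repeated binary outcomes, we will compare the groups using a mixed effects logistic regression model". Otherwise, "if variability is too low, we will use a (non-mixed-effects) logistic regression model to compare the groups on proportion of participants reporting active ideation", counting a participant who does so on one or more occasions.

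The section gives no event count that separates sufficient from too low. It names no test or interval, no exact or penalised method, and no rule for an arm without events. It also does not say whether site enters the fallback model, although Sections 13.4.3 and 13.4.4 do say so for their models. The sample is "90 subjects. 60 randomized to PGB/LFX; 30 to PGB-PLA/LFX", and Section 13.6 analyses all randomized participants.

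**The concern.** The fallback is used only when events are scarce, and that is when one arm may well have none. Ordinary logistic regression estimates the group effect by maximum likelihood. If one arm has no events, the likelihood keeps rising as the log odds ratio moves towards plus or minus infinity, so there is no finite estimate. Dropping the random effect does not cure this.

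At stake is a usable effect size and interval for one of the four listed safety outcomes, for a combination that Section 3.0 says has not been used before. An unnamed test also leaves a choice to be made after the data are seen.

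**Working it through.** **Inputs.** Arms of 60 and 30 (Section 3.0). On-study rate of Q4/Q5 endorsement: not in the documents, so assumed at 0.5% to 10% per participant, equal in both arms. Section 7.5.10 calls suicidal adverse events infrequent and gives a figure of 1%. That comes from alcohol-dependence trials of XR-NTX, so it is no estimate for this contrast. The plan has no figure of its own to reproduce here.

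**Step 1: chance of an empty arm.** With risk p:
- both arms empty: (1−p)^90
- at least one empty: (1−p)^60 + (1−p)^30 − (1−p)^90
- exactly one empty: the second minus the first

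At p = 1%: 0.99^60 = 0.547, 0.99^30 = 0.740 and 0.99^90 = 0.405. At least one empty = 0.547 + 0.740 − 0.405 = 0.882; exactly one = 0.882 − 0.405 = 0.477.

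| Assumed risk | Expected events in 90 | At least one arm empty | Both empty | Exactly one empty |
|---|---|---|---|---|
| 0.5% | 0.45 | 96% | 64% | 33% |
| 1% | 0.9 | 88% | 40% | 48% |
| 2% | 1.8 | 68% | 16% | 52% |
| 3% | 2.7 | 50% | 6% | 43% |
| 5% | 4.5 | 25% | 1% | 24% |
| 10% | 9 | 4% | about 0% | 4% |

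**Step 2: what the fallback returns.** Logistic regression on group and a three-level site factor, with 20 and 10 participants per site, on constructed tables:

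| PGB vs placebo | Log odds ratio | SE | Wald p | Likelihood-ratio p | Fisher p |
|---|---|---|---|---|---|
| 2/60 vs 0/30 | 21.1 | about 22,500 | 0.999 | 0.198 | 0.55 |
| 3/60 vs 0/30 | 20.6 | about 14,500 | 0.999 | 0.115 | 0.55 |
| 8/60 vs 0/30 | 21.7 | about 14,500 | 0.999 | 0.009 | 0.048 |
| 0/60 vs 3/30 | −22.4 | about 16,900 | 0.999 | 0.009 | 0.035 |
| 3/60 vs 1/30 | 0.43 | 1.2 | 0.719 | 0.710 | 1.00 |

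The first four log odds ratios are only where the software stopped iterating; the true maximum is infinite. With an event in each arm (last row) the model behaves normally, so the failure is specific to an empty arm. With 0/60 vs 0/30 the group effect is undefined. The 8/60 row shows only how far two tests from one model can part; it is not an expected result.

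**Step 3: rare-event alternatives on the same data.** Firth-penalised regression with site and group gives an odds ratio of about 2.6 for 2 vs 0 and about 3.6 for 3 vs 0. With no events, the two-sided 95% Clopper-Pearson upper limit is 1 − 0.025^(1/n): 6.0% for n = 60 and 11.6% for n = 30.

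**The case against.** A reader might infer that the analysis would return a p-value near 1 whatever the data, and so conceal a real imbalance. The documents do not support that. Section 13.4.1 specifies no Wald test, and the likelihood-ratio test from the same model gives p = 0.009 for both 8/60 vs 0/30 and 0/60 vs 3/30. The proportions per arm can always be reported.

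Large imbalances with an empty arm are also improbable when events are rare. Across equal risks of 1% to 5%, an empty arm together with Fisher p < 0.05 occurs about 0.2% to 1.1% of the time, so a different test would seldom change the conclusion. Part of the headline probability is the case with no events at all (40 of the 88 points at 1%), where no method gives a meaningful comparison.

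Nor is the exclusion an error. Barring current ideation and then measuring new ideation is ordinary safety practice. It applies at screening, up to 30 days before admission (Section 9.1.1), and the C-SSRS is then given on Days 1 to 8, 10 and 15 (Section 10.11), so ideation that emerges in withdrawal can count. Finally, the DSMB reviews all adverse events with access to unblinded data (Section 19.1), so detecting a safety signal does not rest on this model.

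All of this stands and limits the consequence. It does not supply the missing estimate and interval, or name the test.

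**Conclusion.** The point holds in a narrow form. Section 13.4.1 prescribes a low-event method that has no finite odds ratio or usable Wald interval when one arm is empty, and that is undefined when both are. That this failure is the likeliest result is a further inference the documents do not support: it depends on an unstated rate, and the chance of at least one empty arm falls from 88% at 1% to 25% at 5% and 4% at 10%. These figures assume equal risk in both arms and that all 90 participants contribute.

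The loss is a usable effect size and interval, plus an open choice of test: Wald p = 0.999 or likelihood-ratio p = 0.009 on the same 8/60 vs 0/30 data. This concerns a safety outcome, not the primary or secondary one. It is a modest but nearly free improvement to the plan.

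**What to change.** Replace the fallback sentence in Section 13.4.1 along these lines:

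- If either arm has fewer than a pre-stated number of participants with active ideation (for example 5), report the count per arm and the risk difference with an exact 95% confidence interval.
- Compare the arms by one method named in advance: either Firth-penalised logistic regression with site and group, or an exact test stratified by site.
- If no events occur in either arm, make no comparison and report the exact two-sided 95% upper limits: 6.0% for 0/60 and 11.6% for 0/30.

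The cost is SAP wording and a little extra analysis work, with no new data, visits or participants. The drawback is that exact tests are conservative at these sizes.

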5.0 Table 1. Overview of Study Assessments

Assessment	Outpatient	Inpatient	Inpatient	Inpatient					Inpatient	Outpat	Outpat	EOS/ AMA VISIT (early)
	Screen	Day 1	Day 2	Day 3	Day 4	Day 5	Day 6	Day 7	Day 8/9 [†] (all assessments Done both days Unless otherwise Stated)	Day 10 +2 business days	EOSDay 15 +2 business days	(04)
Informed Consent	1X											
Locator Information	1X									1X		
Medical History	1X											
Physical/Weight	1X										1X	1X
CBC* with Diff and PLT, INR	1X									1X INR Not repeated	1X if no D10 No INR	1X No INR
Blood Chemistry, with Magnesium and Calcium	1X									1X	CMP 1X IF No Day 10	1X No magnesi m
Creatine Kinase	1X								1X (done at D8- only)	ropodiou		1X
Estimated Glomerular Filtration	1X											
Child Pugh Score	1X											
Urinalysis with Reflex Microscopy	1X									1X		1X
Urine Pregnancy Test - F	1X	1X							1X (if done at D8-do not repeat on D9)		1X	1X
UDS	1X	1X							1X	1X	1X	1X

13

Assessment	Outpatient	Inpatient	Inpatient	Inpatient					Inpatient	Outpat	Outpat	EOS/ AMA VISIT (early)
	Screen	Day 1	Day 2	Day 3	Day 4	Day 5	Day 6	Day 7	Day 8/9 [†] (all assessments Done both days Unless otherwise Stated)	Day 10 +2 business days	EOSDay 15 +2 business days	
Fentanyl	1X	1X							1X	1X	1X	1X
xylazine	1X								1X	1X	1X	1X
Alcohol Breathalyzer Test	1X									1X	1X	
HEP B & C	1X											
ECG	1X	1X	1X	1X	1X	1X	1X	1X				
MINI	1X											
Inclusion/Exclusion	1X											
Randomization Form	1X											
Visual Analog Scale for Craving		2X	2X	2X	2X	2X	2X	2X	1X			
Insomnia Severity Index	1X	1X	1X	1X	1X	1X	1X	1X	1X	1X	1X	
SOWS-Gossop	1X	2X	2X	2X	2X	2X	2X	2X	1X	1X	1X	
COWS	1X	2X	2X	2X	2X	2X	2X	2X	2X	1X	1X	
POSS		3X	4X	4X	4X	4X	4X	4X	1X			
Naloxone Challenge (optional; only if pt. is interested and detoxed)									1X (if positive on D8- repeat on D9)			1X Can be given to AMA Pts
XR-NTX									1X (if not done D8- do on D9)			1X Can be given to AMA Pts
Vital Signs Cont'd next pg.	1X	8X	8X	8X	8X	8X	8X	8X	1X BP sitting only	1X BP sitting	1X BP sitting only	1X BP sitting

Assessment	Outpatient	Inpatient	Inpatient	Inpatient					Inpatient	Outpat	Outpat	EOS/ AMA VISIT (early)
	Screen	Day 1	Day 2	Day 3	Day 4	Day 5	Day 6	Day 7	Day 8/9 [†] (all assessments Done both days Unless otherwise Stated)	Day 10 +2 business days	EOSDay 15 +2 business days	
(BP-sitting & standing); Pulse										only		only

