8.2 SECONDARY OBJECTIVES

1) To determine if PGB plus LFX will result in more successful opiate detoxifications Successful detoxification is defined as completing the 7-day regimen/dosing of either PBG/LFX or LFX/PGB-PLA without leaving the inpatient unit or otherwise withdrawing from

the study; having a SOWS score of less than 6; a COWS score of less than 9; and a urine drug screen that is negative for opioids, **excluding buprenorphine**, **and fentanyl**.

2) To determine whether PGB plus LFX improves rates of completion of detox and receipt of XR-NTX

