- 12) Comfort medications given on a PRN schedule

Successful detoxification is defined as (a) not leaving the inpatient unit before day 8; (b) SOWS of 5 or less and COWS of 8 or less; and, (c) urine drug screen negative for opioids, excluding buprenorphine, and fentanyl.

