9.1.3 Phase 3: Inpatient XR-NTX Dosing (Day 8 or 9)

On day 8, subjects will be offered an injection of XR-NTX following naloxone challenge starting with a split dose an option of 0.2 mg first, wait 10-20 minutes, then 0.6 mg (0.8 mg I.M of naloxone total) An injection of Vivitrol is optional, only if the subject is interested in the XR-NTX treatment), and only if the COWS does not rise above 10 (COWS) within 15-30 minutes after the challenge. Subjects will be offered a second XR-NTX dose in the outpatient research clinic 4 to 5 weeks after the Day 8/9 injection if they wish to continue XR-NTX and have been unable to find a community provider. Subjects who fail the naloxone challenge on Day 8 will receive symptomatic treatment, observed until symptoms resolve, and be offered an opportunity for a repeat

challenge and injection on day 9. Note:

Note: XRNT may be given to patients after a Naloxone challenge in Pts about to go AMA from hospital if the naloxone challenge results suggest an absence of physiologic dependence.

The following assessments will be conducted before the XR-NTX injection:

- 1) CK test drawn before IM Injection of naloxone (PGB can elevate CK)
- 2) Vital Signs (blood pressure sitting)
- 3) Adverse Events Review
- 4) Urine Pregnancy Test
- 5) VAS scale
- 6) ISI
- 7) SOWS-G
- 8) POSS
- 9) UDS
- 10) Urine Fentanyl test
- 11) urine xylazine test
- 12) COWS
- 13) Naloxone Challenge*
- 14) Concomitant Medication Review
- 15) C-SSRS

ADMINISTRATION OF EXTENDED-RELEASE NALTREXONE

The following assessments will be conducted after the XR-NTX injection:

- 1) CGI
- 2) HAM-A, HAM-D
- 3) Inspection of injection site
- 4) Comfort medication(s) (PRN)

(It is permissible to give comfort medication at visit 8 for Day 8, 9, and at Day 10 for visit 10, 11, 12, 13, 14 and 15. No comfort medication will be given by the study after Day 15. Comfort medication needed after Day 15 will be considered non-study follow-up care. Patients can get comfort medications even if they don't opt for XR-NTX).

* Optional. Subject can opt not to receive this treatment. The Study Physician will discuss with the subject other available options. All assessments for Day 8 except the challenge and XR-NTX will still be collected.

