11.5 RECEIPT OF NALOXONE

Subjects will be offered a naloxone challenge on day 8 using 0.8 mg or 1.0 mg I.M. If the COWS scores do not rise above 10 within 15-30 minutes, subjects will receive an injection of XR-NTX* given by a study nurse (or NP, etc.), physician (or PA, etc.) or other licensed and trained health care provider. Each site will acquire their own supply of naloxone and will be responsible for the storage, accountability, and dispensing throughout the trial. (*Naloxone challenge and receipt of XR-NTX is optional. Subject can request guidance on another form of treatment).

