12.5 DISPENSING XR-NTX

On day 8 or 9, a 380 mg injection of XR-NTX will be administered according to subjects' consent and evidence that detoxification has been successful, by a negative naloxone challenge. Dosing will be maintained in a Drug Accountability Log and recorded in RedCap. Subjects who are unable to find an outpatient provider will be offered a second dose of XR-NTX up to 5 weeks after day 8 or 9 (day 36 ± 7 days).

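### Section 3.0 requires urine free of fentanyl and buprenorphine before XR-NTX, but sections 9.1.3, 11.5 and 12.5 let the naloxone challenge decide and require no urine result

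*Combined protocol and SAP*

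**What the plan says.** Section 3.0, in the row on study product and regimen, offers XR-NTX on Day 8 to subjects who provide a "urine sample that is negative for opioids, buprenorphine, and fentanyl, and pass a naloxone challenge". The Day 8/9 box of the schematic in 4.0 appears to carry the same condition, though its text is scrambled in the copy reviewed. The Duration row of 3.0 asks only that a urine be given and states no result.

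The sections that govern the injection read differently:

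- Section 11.5: "If the COWS scores do not rise above 10 within 15-30 minutes, subjects will receive an injection of XR-NTX". A footnote makes both the challenge and the injection optional for the subject.
- Section 12.5: the subject's consent and "evidence that detoxification has been successful, by a negative naloxone challenge".
- Section 9.1.3: interest in the treatment, and "only if the COWS does not rise above 10 (COWS) within 15-30 minutes after the challenge". The drug screen and the urine fentanyl test are among the assessments to be done beforehand, but no result is required.

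Three other places bear on the question. Section 7.5.11 says XR-NTX should not go to patients who "failed a naloxone challenge or have a positive urine screen for opioids". Table 1 restricts the challenge itself: "Naloxone Challenge (optional; only if pt. is interested and detoxed". Section 9.1.2 defines successful detoxification to include a "urine drug screen negative for opioids, excluding buprenorphine, and fentanyl". Section 8.2 likewise asks for "a urine drug screen that is negative for opioids" and adds the same qualifier about the two drugs.

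**The concern.** A site needs one rule for who may be injected. Here the answer for a fentanyl- or buprenorphine-positive patient depends on the section consulted.

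Two things are at stake. The first is safety. Section 7.1 says one injection blocks opioid receptors for up to four weeks, and 7.5.2 warns that it will precipitate or worsen withdrawal in a patient who is still dependent. The second is the secondary endpoint. Under 13.3.2, receipt of the first XR-NTX dose separates level 3 from level 2 of the ordinal outcome, so the dosing rule helps to determine what that endpoint measures.

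**Working it through.** No arithmetic applies, so the check is to run one patient through each section. The patient has completed detoxification under 13.3.2 (a Day 7 dose and the Day 7 post-dose SOWS), wants XR-NTX, has a negative opioid screen, passes the naloxone challenge, and tests positive for fentanyl or buprenorphine on Day 8.

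| Section | What decides | This patient |
|---|---|---|
| 3.0, regimen row | Three negative urine findings and a passed challenge | Refused |
| 4.0, schematic (scrambled) | Appears to match 3.0 | Apparently refused |
| 3.0, Duration row | Interest, a urine given, a passed challenge | Can be injected |
| 9.1.3 | Interest, COWS not above 10 after the challenge | Can be injected |
| 11.5 | COWS not above 10 after the challenge | Can be injected |
| 12.5 | Consent, negative challenge | Can be injected |
| 7.5.11 | No opioid-positive urine screen | Unclear |

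Do other sections close the gap?

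1. **Opioids in general.** Mostly yes. Section 7.5.11 makes an opioid-positive screen a contraindication.
2. **Fentanyl and buprenorphine under 7.5.11.** Only arguably. Neither is named there. Section 10.11 lists urine fentanyl (item 12) apart from the drug screen (item 11), and item 11 allows buprenorphine to be a separate added test. Section 3.0 also names the three findings individually.
3. **The Table 1 restriction to detoxified patients.** This leads back to 8.2 and 9.1.2. The word *excluding* there can mean that the two drugs must also be absent, which agrees with 3.0, or that they are not counted, which contradicts it.
4. **Precedence.** No section says which rule governs.

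Consequence for the endpoint: refused, this patient is level 2; injected, level 3. A patient who leaves before Day 7 is level 1 under either rule.

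Size: the affected patients are those who are positive for fentanyl or buprenorphine, pass the challenge and accept the optional injection. The documents give no rate for any of these three, so no estimate is offered.

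**The case against.** The strongest reply is that this is an omission, not a contradiction. No section says that a fentanyl- or buprenorphine-positive patient may be injected, and a site that applies every stated condition satisfies all of them. Section 11.5 is mainly about naloxone supply. It also leaves out the pregnancy test and the other contraindications, so it is not a complete eligibility list. Section 12.5 asks for successful detoxification, which 8.2 and 9.1.2 define with a urine criterion. A positive fentanyl test could naturally be read as a positive urine screen for an opioid under 7.5.11.

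Much of this stands. Section 7.5.11 may cover the two drugs, and a cautious site would reach the 3.0 answer. But 11.5 and 12.5 present the challenge as what decides, and the urine criterion behind 12.5 contains the ambiguous wording. Sites working from the same document could reasonably differ.

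The safeguards common to every version also deserve weight. Section 7.5.2 requires clinical observation and a COWS of 10 or less both before and after naloxone. Section 11.9 treats even slight or passing gastrointestinal symptoms as withdrawal.

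A reader might infer more than the documents support:

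- *That the treatment comparison is biased.* Randomization is blocked within site (11.1), and site is a factor in the ordinal model (13.3.2). Differing site practice does not by itself favour an arm.
- *That the definition certainly disregards the two drugs, or certainly requires their absence.* The text settles neither.
- *That 3.0 is outdated, or that it plainly controls.* Section 3.0 is labelled version 7.0, while a page within 11.9 is marked V9.0. That does not show which rule is current.
- *That patients leaving against medical advice must meet the urine rule.* Sections 7.5.2 and 9.1.3 allow their injection on challenge results. A urine bar would be a new clinical restriction.

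**Conclusion.** The point holds for fentanyl and buprenorphine. The protocol's one explicit urine rule is missing from the sections that direct the injection, and the text that might supply it is either silent on these drugs or ambiguous. The same patient can be refused or injected depending on the section followed. If that patient completed detoxification, the choice moves the secondary outcome by one level.

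The conclusion rests on reading 11.5, 12.5 and 9.1.3 as written, and on 7.5.11 not clearly reaching the two drugs. The schematic is secondary support only, because its text is scrambled. Frequency is unknown, no bias between arms is shown, and the primary SOWS analysis is untouched. The ambiguity should be removed, but it does not undermine the trial's main comparison.

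**What to change.** Unless the sponsor intends otherwise, carry the 3.0 rule through:

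- Add to 9.1.3, 11.5, 12.5 and the Duration row of 3.0: *and the Day 8/9 urine tests for opioids, fentanyl and buprenorphine are all negative, as section 3.0 requires*.
- Name fentanyl and buprenorphine in 7.5.11.
- Have the sponsor confirm what *excluding* means in 8.2 and 9.1.2, and reword both to match.

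If the sponsor means the two drugs to be disregarded, amend 3.0 and the schematic instead, so that one rule governs. Whether any urine rule should apply to patients leaving against medical advice is a separate clinical decision for the sponsor.

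The cost is a wording amendment, submitted to NIDA and the IRB as 18.1 requires. No new tests are needed: Table 1 already schedules the drug screen and urine fentanyl on Day 8/9, and item 11 of 10.11 provides for buprenorphine testing. Somewhat fewer patients may qualify for XR-NTX. If patients have already been dosed, apply the clarified rule from the amendment date and record that date.
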